11.2. Methods

Two-sided tests and a 5% critical value will be used throughout the trial. Test procedures to reduce multiple testing will be applied. Refer to the detailed, separate statistical analysis plan for further information.

11.2.1 Efficacy Analysis

The efficacy analysis will compare changes in the primary and secondary efficacy endpoints described above between the placebo and the DF periods.

The repeated measures analysis of variance (ANOVA) will be used for analysis of treatment and period effects (treatment=independent factor, period=independent factor, outcome variable=dependent factor). When significant, post hoc comparisons will be performed with nonparametric tests for reasons of robustness: The Friedman ANOVA and the Wilcoxon test for post hoc comparisons will be used.

Furthermore, graphs showing the time profiles at the individual subject and group mean levels will be presented.

Multiple parameters will be tested. However, to reduce the number of tests a stepwise statistical analysis plan will be applied. Moreover, this study is of exploratory nature and correcting for multiple testing is therefore not necessary.

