3.1. Flow Chart

3.2. Trial design and rationale

Before initiation of the trial we will investigate the effects of DF on thrombelastometry ex vivo. In this part blood samples will be drawn from a minimum of eight healthy volunteers and after *ex-vivo* spiking of blood samples with increasing doses of DF thrombelastometry will be performed. The effects of activators (i.e. recombinant tissue factor) on DF in thrombelastometry will be investigated. The number of participants may be increased to 16 after analysis of the results of the first eight subjects.

This trial is designed as a randomized, double blind, crossover trial in 20 healthy volunteers. Sixteen healthy volunteers will be randomly assigned to receive LPS, whereas four healthy volunteers will be randomly assigned to the placebo group. In each group two treatment periods will be performed. In one treatment period all subjects will be treated with DF. In the other treatment period all subjects will be treated with placebo. A washout period of 6 weeks will be planned between both treatment periods to reduce the risk of any carry-over effects. Whether a subject starts with the placebo or the DF period will also be randomized.

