5.4. Blood Sampling schedule, tubes and volume

Blood samples will be drawn at predefined time-points. Baseline measurements will be performed before infusion of any trial drug. Total blood volume will not exceed 240ml per period.

Table 1. Parameters, Samples and Schedule

Parameter	Sample	Time points
Coagulation biomarkers	Citrated plasma	Pre, 0h, 1h, 2h, 4h, 6h, 24h
Fibrinolysis biomarkers	Citrated plasma	Pre, 0h, 1h 2h, 4h, 6h, 24h
Endothelial biomarkers	EDTA-plasma/ Citrate plasma	Pre, 0h, 1h 2h, 4h, 6h, 24h
Inflammatory biomarkers	EDTA-plasma, Serum, Citrate-plasma	Pre, 0h, 1h 2h, 4h, 6h, 24h
FACS analysis	Citrated blood	Pre, 0h, 1h 2h, 4h, 6h, 24h

MPTF	Citrated plasma	Pre, -0h, 2h, 4h, 6h, 24h
Chemistry	Serum	Pre, 24h
Differential blood counts	EDTA	Pre, 0h, 1h 2h, 4h, 6h, 24h
Global coagulation assays	Citrate	Pre, 0h, 1h 4h, 24h
LPS quantification	Citrate	0h, 5min ,10min, 20min

Pre= Before Defibrotide/Placebo infusion and before LPS, 0h=Before LPS injection, other time-points relate to the LPS injection

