11.1. Sample Size Calculation

The sample size calculation is based on the experience with prior trials using anti-coagulants in the human endotoxemia model. Ten to 15 subjects in each group were sufficient to detect significant differences in the primary outcome parameter (F1+2 levels) between treatment groups in a parallel-group study^{14,23,24}. Currently, we do not have a good estimate for the size of effect of defibrotide in the same model. In a prior LPS trial F1+2 levels of approximately 819 ± 173 (Standard deviation) pmol/ml were measured ⁴¹. This corresponds to an approximate 6fold increase in F1+2 levels and was similar in other endotoxemia trials⁴². The median intraindividual coefficient of variation was 15% in a recent study, the mean was 25%³². Thus, a sample size of 16 volunteers will be sufficient to detect a 25% decrease in the defibrotide period.

The placebo group consisting of four healthy volunteers will be an additional control group, which will also allow to assess the effects of DF in healthy volunteers without LPS. However, this analysis is exploratory and no sample size calculation for this group is performed.

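### The efficacy analysis compares undefined changes with no pre-dose covariate and no log scale; fixing both costs almost nothing, and the gain depends on what change means

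*Combined protocol and SAP*

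**What the plan says.** Section 11.2.1 (Efficacy Analysis) sets the comparison: "The efficacy analysis will compare changes in the primary and secondary efficacy endpoints described above between the placebo and the DF periods". The method is a repeated-measures ANOVA with treatment and period as factors. If it is significant, Friedman and Wilcoxon tests follow. No baseline covariate and no transformation is named there or elsewhere in the supplied text. Section 5.2.1 words the primary endpoint as levels of F1+2, not as a change.

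Section 5.4 provides for a baseline in each period: "Baseline measurements will be performed before infusion of any trial drug". Its Table 1 separates Pre, taken before the DF/placebo infusion, from 0h, taken before the LPS bolus.

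Section 11.1 plans almost wholly in multiplicative terms: an intraindividual CV (median 15%, mean 25%), a rise described as "This corresponds to an approximate 6fold increase in F1+2 levels", and the claim that "a sample size of 16 volunteers will be sufficient to detect a 25% decrease in the defibrotide period".

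Section 11.2 refers to a separate statistical analysis plan for detail. Its text is not part of the supplied document.

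**The concern.** Three things are left open: what a change is, on which scale it is analysed, and how the pre-dose sample enters.

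- Subtracting a baseline carries that baseline's full error into the treatment contrast. Using it as a covariate lets the data decide how much of it to remove.
- A percentage effect and a CV are naturally read on the log scale, where the treatment contrast is a DF/placebo ratio. An ANOVA on untransformed values does not estimate the quantity that the sample size was planned for.
- The same wording governs every secondary endpoint, including markers that may rise far less than F1+2.

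At stake is the width of the confidence intervals from 16 subjects, and whether the primary result can be set directly against the planned 25% decrease.

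**Working it through.** **Inputs from the documents.** N=16 in the LPS group and a 25% decrease (Section 11.1); within-subject CV 25% (mean) or 15% (median) (Section 11.1); two-sided 5% (Section 11.2: "Two-sided tests and a 5% critical value will be used throughout the trial"); two-period crossover with randomised order (Section 3.2: "Whether a subject starts with the placebo or the DF period will also be randomized"). For the baseline: "In a prior LPS trial F1+2 levels of approximately 819 ± 173 (Standard deviation) pmol/ml were measured", about six times the pre-dose value, so the pre-dose mean is about 819/6 = 136.5.

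**Assumptions not in the documents.** 80% power; rho; equal log variance before and after LPS; between-subject CV 15%; lognormal data; one post-LPS time point.

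**1. The plan's own figure.** With the SD of the within-subject difference equal to sqrt(2) x CV,

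n = 2 x [0.25 x (1.960 + 0.842) / 0.25]^2 = 15.7, rounded up to 16.

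So N=16 reproduces at CV 25% if 80% power was intended. This formula describes a level. It makes no allowance for baseline error.

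**2. Variance relative to a post-LPS level.** Let k = SD(pre)/SD(post).

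- Change score: 1 + k^2 - 2 x rho x k
- Covariate: 1 - rho^2

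On the log scale k = 1, so change over covariate is 2(1 - rho)/(1 - rho^2) = 2/(1 + rho): 2.00, 1.54, 1.33 and 1.18 at rho 0, 0.3, 0.5 and 0.7.

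For raw F1+2, k = 1/6, so the change score gives 1 + 1/36 - rho/3: 1.028, 0.928, 0.861 and 0.794. The covariate gives 1.00, 0.91, 0.75 and 0.51. The two differ little until rho is high.

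**3. One case by formula: log scale, rho 0.3, CV 25%.** Effect = -ln(0.75) = 0.288. Log variance = ln(1 + 0.25^2) = 0.0606.

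- Log change: SE = sqrt(2 x 0.0606 x 1.40 / 16) = 0.103; 0.288/0.103 = 2.79; power 79.8% by normal approximation, 73.8% by t with 14 df.
- Log covariate: SE = sqrt(2 x 0.0606 x 0.91 / 16) = 0.083; 0.288/0.083 = 3.46; power 93.4% by normal approximation, 89.2% by t with 13 df.

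Simulation also charges for estimating the covariate slope, which brings 89.2% down to about 87%.

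**4. Simulated power (%), N=16, CV 25%, 25% decrease, period in the model, 20,000 runs.**

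| rho | Raw level | Raw change | Log or fold change | Log level with log Pre covariate |
|---|---|---|---|---|
| 0 | 84.8 | 83.7 | 58.3 | 83.6 |
| 0.3 | 85.1 | 87.7 | 73.6 | 86.9 |
| 0.5 | 84.7 | 90.2 | 86.3 | 92.0 |
| 0.7 | 85.3 | 92.8 | 97.9 | 98.4 |

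Covariate minus raw change: -0.1, -0.8, +1.8 and +5.6 points. Covariate minus log change: +25.3, +13.3, +5.7 and +0.5 points.

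At CV 15%, raw change and the covariate analysis both reach at least 99.7%. Log change reaches 94.7% at rho 0 and 99.0% or more from rho 0.3.

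**5. A marker that is not protected by a large rise.** If baseline spread is close to post-LPS spread, k is near 1 on the raw scale too, and the factor 2/(1 + rho) applies there. For an illustrative marker with pre-dose values similar to its placebo post-LPS values, CV 25%, a 25% decrease and rho 0.3, power is about 64% for raw change and 87% for the log covariate analysis.

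**The case against.** **The stronger reading.** A reader might infer that the plan throws away a substantial part of its precision on F1+2. The documents do not support that. The large losses belong to a log or fold change score, and Section 11.2.1 states neither. If a change is an ordinary difference, the roughly sixfold rise makes the baseline a small part of the contrast, and the fix gains little unless rho is high. At the median CV of 15%, raw change and the fix are both near certain to detect a 25% decrease. The crossover has also already removed between-subject variation. All of this stands.

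**Baseline may not be subtracted at all.** Section 5.2.1 speaks of levels, so an ANOVA on post-LPS values is a possible reading. Then no baseline error is added, and against raw levels the covariate changes power by between about -1 point (rho 0) and +13 points (rho 0.7). This too stands, and it shows that the text does not settle which analysis is meant.

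**The separate plan may settle it.** It may. Silence here is not exclusion, but content that cannot be seen cannot be credited.

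**Secondary markers.** The documents give no baseline, CV or correlation for any of them, so the 64% against 87% is an illustration, not an estimate for a named marker.

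**Robust follow-up tests.** The Wilcoxon test partly answers skewness, but only after a significant ANOVA. It neither adjusts for baseline nor yields the planned percentage effect.

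**Conclusion.** The point holds as a gap in specification with a nearly free improvement. It is not a demonstrated loss on the primary endpoint. The size depends on the reading:

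- **Log or fold change:** a large loss at low correlation (58% against 84% power at rho 0, 74% against 87% at 0.3), smaller at 0.5 (86% against 92%) and none to speak of at 0.7.
- **Raw change in F1+2:** about -1 to +2 points from the fix for rho up to 0.5, and about +6 at 0.7.
- **Secondary markers with similar spread before and after LPS:** a larger loss than for F1+2, of unknown size.

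The comparisons are for CV 25% and rest on an undocumented rho, equal log variance before and after LPS, lognormal data and a single time point. Whatever rho is, the log covariate analysis is never far behind raw change and guards against the worst case. It also gives a result on the scale of the planned 25% decrease.

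**What to change.** State in Section 11.2.1, or in the separate analysis plan before unblinding:

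- The outcome is the log of the post-LPS value, not a change score.
- The model contains treatment, period and subject, with the log Pre value of the same period as covariate. With subject effects in the model, a separate subject-mean covariate is not needed.
- The covariate is Pre and not 0h. Under Section 3.3.3 the DF/placebo infusion starts one hour before LPS, so 0h may already carry a treatment effect.
- The result is reported as the DF/placebo ratio with its 95% CI.

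Make both changes together: moving to a log change score without the covariate can lose power. If the sponsor prefers another analysis, define the change and its scale and give the reason.

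The cost is a few lines of text and about one residual degree of freedom (14 to 13 in the complete 16-subject comparison at one time point). No new samples, subjects or procedures are needed.

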6.4. Randomization and Blinding

All screened subjects will receive a screening number. This number will be the identifier of each subject within the trial. A subject identification list, which links the screening numbers with the names and birth dates of each participating subject will be kept in the trial master file and in the “study maker” (the computer system of the Department of Clinical Pharmacology). In future publications we will only refer to numbers of subjects, but not to names or birth dates.

A physician not performing other tasks in the trial will observe the subjects.

Block randomization will be performed using an open access randomization generator (www.randomization.com).

Three sets of sealed code/label with the randomization number containing information about the treatment allocation (LPS or placebo group, DF or placebo period) for the particular subject will be prepared for each subject.

The code for a particular subject can be broken in a medical emergency if knowing the identity of the treatment allocation would influence treatment of the subject. Whenever a code is broken, the person breaking the code must record the time, date and reason as well as their initials in the source documents.

All codes (whether broken or not) must be kept throughout the trial period.

Breaking of the code, however, does not necessarily mean that the plasma obtained from the subject is not eligible for analyses, which can still be performed in a blinded fashion.

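### The post hoc Wilcoxon and Friedman tests carry no stated period term, so as paired DF-minus-placebo tests they can fail to confirm an effect found by the period-adjusted ANOVA, and no rule says which result stands

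*Combined protocol and SAP*

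**What the plan says.** The trial is a two-period crossover with randomised order (section 3.2): "Whether a subject starts with the placebo or the DF period will also be randomized". Section 11.2.1 sets the first analysis: "The repeated measures analysis of variance (ANOVA) will be used for analysis of treatment and period effects". The factors it lists are treatment and period. If that analysis is significant, nonparametric post hoc comparisons follow, and the reason given is robustness: "The Friedman ANOVA and the Wilcoxon test for post hoc comparisons will be used".

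The section describes efficacy as a comparison of the placebo periods with the DF periods. It does not state:
- whether Wilcoxon means the signed-rank or the rank-sum test;
- whether Friedman is applied across the two treatments or across sampling times;
- which ANOVA effect must be significant before the post hoc step;
- what is concluded if the two steps disagree.

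Section 11.2 fixes the level, "Two-sided tests and a 5% critical value will be used throughout the trial", and refers to a separate statistical analysis plan that is not part of the text reviewed.

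**The concern.** Period is in the ANOVA because order is randomised and levels may differ between the first and second challenge. The natural reading of the second step is a paired test of DF minus placebo within subject, and that test drops period again. In one sequence the paired difference contains treatment plus period, in the other treatment minus period. A period effect then spreads the differences apart and weakens the test.

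Treatment has only two levels, so for the overall DF-placebo contrast the second step asks the ANOVA's question again with less adjustment. It runs only after a significant ANOVA, so it can cast doubt on a finding but can never recover one that the ANOVA missed through skewness or outliers. That is not the protection a robust analysis is meant to give. At stake is a report on F1+2, or on any secondary marker, with two p-values that disagree on the same question and no rule written in advance to resolve it.

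**Working it through.** **Inputs from the documents.** Two-sided 5% (11.2); 16 LPS subjects and a 25% decrease (11.1); intraindividual CV of 15% (median) or 25% (mean) (11.1); randomised order (3.2); block randomisation (6.4).

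**Assumed.** Split 8:8, because block size and sequence split are not stated. Normal errors on the log scale, no carry-over. The period effect is varied because the documents give none.

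**The plan's own figure.** Section 11.1 concludes: "Thus, a sample size of 16 volunteers will be sufficient to detect a 25% decrease in the defibrotide period". Power is not stated. With 80% assumed and CV 25%, the paired normal approximation gives n = 2 × [0.25 × (1.960 + 0.842) / 0.25]² = 2 × 7.85 = 15.7, so 16. The figure reproduces.

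**Structure.** Let τ be the log treatment effect and π the log period effect (period 2 minus period 1).
- DF minus placebo: τ + π if placebo came first, τ − π if DF came first.
- Period 2 minus period 1: π + τ and π − τ. The difference between sequences is 2τ, so π cancels.

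**Spread.** The SD of a within-subject log difference is √(2 ln(1 + CV²)): 0.348 at CV 25% and 0.211 at CV 15%. In a paired test at 8:8, the variance becomes this SD squared plus π². At CV 25%:
- 25% rise, π = ln 1.25 = 0.223: √(0.1213 + 0.0498) = 0.414.
- 25% fall, π = ln 0.75 = −0.288: √(0.1213 + 0.0828) = 0.452.

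The fall is the larger effect on the log scale; it equals a rise of one third.

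**Power by simulation** (CV 25%, 8:8, true effect ln 0.75; repeat runs differ by up to about a point):

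| Assumed period effect | ANOVA with period | Paired Wilcoxon | Rank-sum on period differences | ANOVA significant, Wilcoxon not |
|---|---|---|---|---|
| none | 87% | 84–85% | 84–85% | 3% |
| 15% rise | 87% | 79–80% | 84–85% | 8% |
| 25% rise | 87% | 71–72% | 84–85% | 15–16% |
| 25% fall | 87% | 62% | 84–85% | 25% |

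If Friedman is used across the two treatments, it is a sign test. Its power is about 79% with no period effect, 64% with a 25% rise and 53% with a 25% fall.

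**CV 15%.** ANOVA power is 99.9%. Paired Wilcoxon has 99.8% with no period effect, about 96% with a 25% rise and about 88% with a 25% fall: losses of about 4 and 12 points.

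**Type I error (CV 25%, 8:8).** Paired Wilcoxon alone rejects in about 4.3% of null trials with no period effect, 1.8% with a 25% rise and 0.9% with a 25% fall. The rank-sum test stays near 5%.

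**Unequal sequences (6:10, CV 25%, period effect against DF).** The power of ANOVA followed by Wilcoxon is 82% with no period effect, 74% at +10%, 60% at +20% and 41% at +30%. Its type I error is at most 0.033.

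**The case against.** The strongest reply is that the text is open. It calls the nonparametric tests post hoc and never says that they override the ANOVA. Wilcoxon could mean a rank-sum test on period differences, which would adjust for period. Friedman could be meant for the time course, since section 5.4 lists seven sampling points for coagulation markers; on that reading the two-treatment Friedman figures do not apply. The separate analysis plan may settle all of this. The study calls itself exploratory, and block randomisation makes marked imbalance unlikely. All of this stands, and it limits the point to what is unstated and to a conditional loss of power. It does not remove the point: section 11.2.1 names the tests without adjustment and gives no precedence. The exploratory label is used there to waive multiplicity correction, a different matter.

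Three stronger readings are tempting and are not supported:
- **That these tests decide DF against placebo.** The text does not say so; it is silent on precedence.
- **That false positives increase.** At 8:8 the paired tests become more conservative as the period effect grows. If the treatment effect opens the gate, the two-step route cannot exceed the ANOVA's 5%. A two-treatment Friedman test used alone does have true size 2 × 2517/65536 = 7.7% at n = 16, but that comes from the discreteness of the test, not from period. Behind a treatment-effect gate its size is about 3%.
- **That the error rates are certainly wrong.** That needs a period effect, and the documents report none. The six-week washout (3.2) and batch analysis of stored samples (5.5.2) reduce some sources of one, though not all.

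**Conclusion.** The point holds as an inconsistency with a conditional cost. The plan adjusts for period at the first step, states no such adjustment at the second, and does not rank the two. If the post hoc tests are paired DF-minus-placebo tests, the loss against the ANOVA at CV 25% and 8:8 is 2 to 3 points with no period effect, about 7 with a 15% rise, about 15 with a 25% rise and about 25 with a 25% fall. At CV 15% it is minor unless the period effect is large. These figures rest on log-normal data, balanced sequences, no carry-over and an assumed period effect. The reading of Wilcoxon as a paired test is likely from the wording but is not stated.

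**What to change.** In section 11.2.1:
1. State that the period-adjusted ANOVA treatment contrast is the deciding result.
2. For the robust check of DF against placebo, name the Wilcoxon rank-sum test on within-subject period differences (period 2 minus period 1) between the two sequences, with the Hodges-Lehmann estimate. The shift between sequences is 2τ, so the estimate is halved to give the treatment effect.
3. Report this check beside the ANOVA whether or not the ANOVA is significant.
4. Limit Friedman to the time course within a period.

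This costs wording only: no extra subjects, samples or assays. At 8:8 with no period effect, power against paired Wilcoxon is unchanged within simulation error. If the sequences end unequal and there is no period effect, the exact rank-sum test gives up a little: 82% against 84% at 7:9, and 80% against 84% at 6:10. Keeping the blocks balanced by sequence avoids most of that.

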11.3. Safety Analysis

All subjects who will receive trial drugs (including placebo) will be included in the safety analysis, which will compare the safety endpoints specified above between treatment periods. Tables of summary statistics will be presented. Detailed analysis specifications will be presented in a statistical analysis plan prior to analysis.

As LPS-infusion is associated with a number of adverse effects, particular interest will be focused on potential specific adverse effects of DF such as bleeding events or allergic reactions.

11.4. Missing, unused and spurious data

Missing or spurious data will not be interpolated, but set missing. Statistical analyses will be performed for the intention to treat and the per-protocol population and compared. If results differ significantly it will be mentioned in any reports of trial results.

12. Ethics

The trial will be conducted in accordance with the Declaration of Helsinki for biomedical research involving human subjects.

